7.2 Enrollment and Assignment of Subject Numbers

After the investigator has assured that the subject meets all of the enrollment criteria, the screening and enrollment case report forms will be completed. Note that with respect to Factor VIII coagulant activity (Factor VIII:C) and the Factor VIII inhibitor levels, the values obtained by the central reference laboratory will determine the subject's eligibility. The investigator may use the results from the local laboratory of the site to support clinical decisions in patient management.

After assuring that the subject meets all of the enrollment criteria, the following clinical and laboratory assessments will be performed:

1. Abbreviated physical examination including: interim medical history, vital signs (pulse, respiratory rate, oral temperature, blood pressure) and weight.
2. **If the subject has been treated with any of the products mentioned above in Section 7.1 (cryoprecipitate, Factor VIII concentrate or any other blood product) after the screening tests are performed**, blood will again be drawn no more than three days prior to the first treatment with Alphanate® for baseline testing of the following parameters:
 - (a) Factor VIII coagulant activity (Factor VIII:C) for central lab testing,
 - (b) Factor VIII inhibitor levels (BU/mL) for central testing,
 - (c) Repeat viral and serological tests including anti-HIV-1/HIV-2, HBsAg, anti-HAV, anti-HBV, and anti-HCV, and anti-parvovirus B1.
3. A sample of venous blood will be drawn from which approximately 5 mL of serum will be prepared and aliquoted into three vials of at least 1.5 mL of sample each. The samples will be frozen and retained at -20°C in the event that they are required for later serological or virology tests.

In order to complete subject enrollment and receive the Subject Number, the participating study site will provide to the clinical monitor at Grifols Inc. a copy of the completed screening and enrollment CRFs, screening and enrollment tests and medical history. The results of the screening and enrollment tests and procedures will be reviewed and the clinical monitor will confirm the individual's eligibility and assign a subject number. Grifols Personnel assigned to the study can be contacted by telephone during working hours (8:00 a.m. to 5:00 p.m. Central Time) at [REDACTED] or fax [REDACTED].

Contains Confidential and Proprietary Information of Grifols Inc.

7.3 At seven to fourteen days after the first infusion of Alphanate®

1. Parvovirus B19 PCR assay - only in subjects seronegative for parvovirus B19 at enrollment.
2. Collect a 2 mL sample of citrated plasma for inhibitor testing at the central reference laboratory.

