7.4 Every 3 Months until Month 30 and/or Off-Study

Samples for quarterly testing will be drawn \pm **10 days** of the scheduled visit date. At each of these visits, the following procedures will be performed:

1. Abbreviated physical examination including: interim medical history, vital signs (pulse, respiratory rate, oral temperature, blood pressure) and weight;
2. Factor VIII coagulant activity (Factor VIII:C);
3. Factor VIII inhibitor levels (BU/mL) in two sets of samples;
4. Hematologic status will be assessed by: complete blood count (CBC) with white blood cell (WBC) differential and platelet count.
5. Serum chemistry tests including: alanine aminotransferase (ALT), aspartic aminotransferase (AST), alkaline phosphatase (AP), lactic acid dehydrogenase (LDH), blood urea nitrogen (BUN), creatinine and total bilirubin;
6. Viral and serological tests including: testing for HBsAg, and for antibodies to HAV, HBcAb, HBsAb, HCV, HIV-1/HIV-2 (only if seronegative at baseline) and parvovirus B19 by routine immunoassay (only in subjects who are seronegative at baseline);
7. A sample of venous blood will be drawn from which approximately 5 mL of serum will be prepared and aliquoted into three vials of at least 1.5 mL of sample each. The samples will be frozen and retained at -20°C in the event that they are required for later serological or virology tests.

If at any quarterly visit, **the subject tests positive for the presence of Factor VIII inhibitors (inhibitor titer of greater than 0.6 modified BU/mL), based upon the value determined by the central reference laboratory**, the procedures specified in section 7.12 (Subjects Who Develop Inhibitors) will also be performed.

Contains Confidential and Proprietary Information of Grifols Inc.

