7.5 Unscheduled Visits

For each unscheduled visit, the following tests will be performed:

1. Abbreviated physical examination including: interim medical history, vital signs (pulse, respiratory rate, oral temperature, blood pressure) and weight;
2. Factor VIII coagulant activity (Factor VIII:C);
3. Factor VIII inhibitor levels (BU/mL) in two sets of samples **(to be performed only if: a) there is clinical indication that the normal dosage of Alphanate® is not providing adequate hemostasis, or b) surgery;**
4. Hematologic status will be assessed by: complete blood count (CBC) with white blood cell (WBC) differential and platelet count;
5. Serum chemistry tests including: alanine aminotransferase (ALT), aspartic aminotransferase (AST), alkaline phosphatase (AP), lactic acid dehydrogenase (LDH), blood urea nitrogen (BUN), creatinine and total bilirubin;
6. Viral and serological tests **(to be performed only if subject exhibits clinical or subjective symptoms indicating possible viral infection)** including: testing for HBsAg, and for antibodies to HAV, HBcAb, HBsAb, HCV, HIV-1/HIV-2 (only if seronegative at baseline) and parvovirus B19 by routine immunoassay (only in subjects who are seronegative for parvovirus B19 at baseline);
7. A sample of venous blood will be drawn from which approximately 5 mL of serum will be prepared and aliquoted into three vials of at least 1.5 mL of sample each. The samples will be frozen and retained at -20°C in the event that they are required for later serological or virology tests.

If at an unscheduled visit, a test for Factor VIII **is positive for the presence of Factor VIII inhibitors (inhibitor titer of greater than 0.6 modified BU/mL), based upon the value determined by the central reference laboratory**, the procedures specified in section 7.12 (Subjects Who Develop Inhibitors) will be performed.

Contains Confidential and Proprietary Information of Grifols Inc.

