7.11 Subjects Who Develop Inhibitors

If at any quarterly visit, the subject tests positive for the presence of Factor VIII inhibitors, (inhibitor titer of 0.6 modified BU/mL or greater) based on the local lab test and confirmed by the central reference laboratory test result, the following steps should be taken:

- For an inhibitor titer of greater than or equal to 10 BU/mL,
 - Collect a 10 mL sample of citrated plasma and send to the central reference laboratory.
 - Withdraw the subject only after performing all required testing (see Section 7.4) and only after receiving confirmation of the inhibitor titer from the central reference laboratory.
- For an inhibitor titer less than 10 BU/mL,

Contains Confidential and Proprietary Information of Grifols Inc.

- Collect a 50 mL sample of citrated plasma. This sample can be obtained in multiple draws within a two-week period and sent to the central reference laboratory.
- Repeat inhibitor titer assay at two-week intervals until:
 1. the inhibitor titer decreases to < 0.6 modified BU/mL or
 2. the subject's participation in the study is ended or
 3. it becomes apparent that, after repeated assays at two-week intervals, the inhibitor titer will not decrease during the course of the study (the investigator should first consult with the Project Manager prior to making this determination).
 - If the subject's inhibitor level is less than 5 BU/mL and treatment with Alphanate® at higher doses remains effective in achieving hemostasis, then the subject will continue the current treatment regimen and testing will be performed as described in Section 7.4 above.
 - If Alphanate® treatment either becomes ineffective in achieving hemostasis, even if the inhibitor titer remains below 5 BU/mL, or if the inhibitor level rises to greater than or equal to 5 BU/mL, as confirmed by test results from the central reference laboratory, then the subject will be withdrawn from the study.

Subjects withdrawn from the study may either be treated with alternate concentrates or commence a treatment program with Alphanate® for the induction of immune tolerance. The treating physician, in consultation with Grifols Office of Medical Affairs, will determine the alternate treatment or product and the immune tolerance protocol.

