9.2 Planned Method of Analysis

9.2.1 Primary Endpoint

Incidence of Antibody Inhibitors to Factor VIII in Individuals Treated with Alphanate[®]

Assuming a maximum biannual rate of inhibitor incidence of three percent in multi-transfused hemophilia patients, the 95% one-sided confidence interval for this incidence rate in a sample of 50 subjects is up to two percent. Thus,

Contains Confidential and Proprietary Information of Grifols Inc.

with a sample of 50 evaluable subjects monitored for two years, if one subject develops an antibody inhibitor to Factor VIII with a titer higher than 0.6 modified BU/mL, that persists for at least one month, the incidence of inhibitors to Factor VIII will be judged to be higher than that for patients with hemophilia A who are treated with currently marketed Factor VIII concentrates. If the sample size is increased to 80 subjects, no more than 1 subject may develop an antibody inhibitor to Factor VIII.

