7.2 Visit Windows

Study periods will be windowed as follows:

- Post-Infusion # 1 – 7 to 14 days after infusion
- Quarterly Visits - ± 10 days

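### A low-titre positive in the day 7–14 inhibitor sample starts no repeat titres, so a subject who is negative again at Month 3 cannot be classified against the one-month persistence condition

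*Protocol*

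**What the plan says.** **The early sample.** Protocol 7.3 ("At seven to fourteen days after the first infusion of Alphanate") asks the site to "Collect a 2 mL sample of citrated plasma for inhibitor testing at the central reference laboratory". It adds a parvovirus PCR for seronegative subjects and says nothing about a positive titre.

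**What starts repeat titres.**
- Protocol 7.11 opens with "If at any quarterly visit, the subject tests positive for the presence of Factor VIII inhibitors" and makes the finding "based on the local lab test and confirmed by the central reference laboratory test result". For titres below 10 BU/mL it then repeats the assay every two weeks.
- Protocol 7.4 refers to the inhibitor procedures after a central positive at a quarterly visit.
- Protocol 7.5 does the same after a central positive at an unscheduled visit ("If at an unscheduled visit, a test for Factor VIII" and following). It allows the inhibitor test at such visits only for inadequate hemostasis or surgery.
- In Appendix 2 and SAP 3.2, footnote 4 (two-weekly repeats) is marked only on the quarterly inhibitor cell. The day 7–14 inhibitor cell carries no footnote.

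**What counts as a case.** Protocol 9.2.1 and SAP 4 count an inhibitor "with a titer higher than 0.6 modified BU/mL, that persists for at least one month". At 50 evaluable subjects one such case gives an adverse verdict; at 80 one is tolerated. SAP 9.1 summarizes the presence or absence of inhibitors, with no persistence or titre condition.

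**The concern.** The decision rule needs evidence on duration. The protocol has a procedure that supplies it, namely repeat titres every two weeks, but none of the written triggers reaches the first post-exposure sample. If that sample is positive at a low titre and the Month 3 sample is negative, the inhibitor may have lasted days or more than two months, and no scheduled measurement separates the two.

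The rule turns on single subjects. An unclassifiable subject decides the verdict at 50 if nobody else qualifies. At 80 it uses the allowance, or exceeds it if one other subject qualifies. The two documents could also report the same subject differently: a case by presence in SAP 9.1, and undetermined under Protocol 9.2.1 and SAP 4.

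**Working it through.** **The plan's own figures.** The documents state no interval between the early sample and the next titre, so there is none to reproduce. The only figure attached to the decision rule is a one-sided 95% limit of 2% for 50 subjects. It does not reproduce: 1/50 = 2%, whereas the exact upper limit with 0 of 50 is 1 − 0.05^(1/50) = 5.8%. Nothing below uses it.

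**Inputs.**
- Early sample: day 7 to 14 after first infusion (Protocol 7.3).
- Next scheduled titre: the first visit under "Every 3 Months until Month 30 and/or Off-Study" (Protocol 7.4). The date from which months are counted is not stated.
- Window: "Quarterly Visits - ± 10 days" (SAP 7.2; same in Protocol 7.4).
- Assumption: Month 3 is day 91 from first infusion. Varied to 90 and 92 days, and to a count starting 3 days before first infusion.

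**Gap to the next scheduled titre.**
- Shortest = (Month 3 − 10) − 14; longest = (Month 3 + 10) − 7.

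| Month 3 | Counted from first infusion | Counted from 3 days before |
|---|---|---|
| 90 days | 66 to 93 | 63 to 90 |
| 91 days | 81 − 14 = 67 to 101 − 7 = 94 | 64 to 91 |
| 92 days | 68 to 95 | 65 to 92 |

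Over all variants the gap is 63 to 95 days, always more than twice one month.

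**What can be classified** (central titre above 0.6 and below 5 BU/mL at day 7–14):
- Positive again at Month 3: two positives at least 63 days apart, and the Month 3 positive itself starts two-weekly repeats. This subject can be scored.
- Negative at Month 3: under the 91-day assumption, the time above threshold after the first positive lies anywhere from 0 to 67–94 days. One month falls inside that range, so the subject cannot be scored either way.

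**With the existing two-weekly repeats.** Titres would fall 14, 28 and 42 days after the positive, on study days 21–28, 35–42 and 49–56. Persistence for one month would be settled 28 to 42 days after the positive. The uncertainty about when the titre fell shrinks from 67–94 days to 14.

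**The case against.** Several points on the other side are sound.

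- **Early positives in general.** A reader might infer that no day 7–14 positive can be scored. The documents do not support that. A subject positive at both visits is classifiable. At 5 BU/mL or more, the evaluability rule in Protocol 8.1 and the discontinuation rule in 7.14 apply at any visit and carry no persistence condition. An unscheduled titre is also possible if hemostasis is inadequate.
- **Central-only testing.** A reader might take this as the defect. It is not: Protocol 7.8 bases the primary endpoint on central results alone, and the triggers in 7.4 and 7.5 use the central value. It matters only because 7.11 starts from a local positive. Nor is it certain that no local sample exists, since 7.8 describes duplicate samples at every time point. Sections 7.3 and 7.8 conflict here.
- **Footnote 4.** Its wording covers any subject who develops an inhibitor, so a site might apply it to an early positive. That stands, but the footnote is not attached to this cell, and the measurability of the decision rule should not rest on a site's reading.
- **Direction of bias.** A reader might infer a bias in favor of the product. No passage says that unproven persistence is scored as no case, and SAP 9.1 could count the subject as positive. The direction is open.
- **Purpose and frequency.** The rationale concerns new antigenic sites and does not mention early onset. The documents give no rate for early, transient, low-titre inhibitors, so how often this would arise cannot be estimated.

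None of this supplies a written trigger for the early sample.

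**Conclusion.** The point holds for one kind of subject: central titre above 0.6 and below 5 BU/mL at day 7–14, negative at Month 3, with no clinically prompted titre in between. As written, no titre is scheduled for 67 to 94 days (63 to 95 across the anchors tried), and the one-month condition in Protocol 9.2.1 and SAP 4 cannot be judged. The interval rests on an assumed Month 3 anchor, but no variant brings it near one month.

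One such subject can settle the verdict at 50 and takes the whole allowance at 80; the effect on the verdict is conditional on the subject occurring. A gap in classification is shown, but no bias in a known direction. The amendment is worth making because the protocol already has the measurement needed and its triggers leave this sample out.

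**What to change.** 1. **Protocol 7.3:** state that a central titre above 0.6 modified BU/mL in this sample starts the existing two-weekly repeat titres.
2. **Protocol 7.11:** extend the repeat-titre trigger to any visit, including day 7–14, and let the central value alone start the repeats, as 7.4 and 7.5 do. Otherwise the local-positive clause would block item 1. Align the threshold too: 7.4 and 7.5 use above 0.6, 7.11 uses 0.6 or more. Correct the cross-references in 7.4 and 7.5, which cite 7.12 for procedures found in 7.11.
3. **Appendix 2 and SAP 3.2:** attach footnote 4 and the plasma-volume footnote (7) to the day 7–14 inhibitor cell.
4. **Reconcile 7.3 with 7.8:** say whether a local duplicate is taken at day 7–14. Also say how the condition that Factor VIII be at or below baseline is checked, since no Factor VIII:C is scheduled at that visit.
5. **Reconcile Protocol 9.2.1 and SAP 4 with SAP 9.1:** say whether persistence is part of the primary endpoint, how many days make one month, and how a subject with undetermined persistence is reported.

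No change to withdrawal or dosing rules is proposed. The cost is wording in a few sections and the two schedules, plus a few extra draws, only in a subject with an early positive.

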7.4 Every 3 Months until Month 30 and/or Off-Study

Samples for quarterly testing will be drawn \pm **10 days** of the scheduled visit date. At each of these visits, the following procedures will be performed:

1. Abbreviated physical examination including: interim medical history, vital signs (pulse, respiratory rate, oral temperature, blood pressure) and weight;
2. Factor VIII coagulant activity (Factor VIII:C);
3. Factor VIII inhibitor levels (BU/mL) in two sets of samples;
4. Hematologic status will be assessed by: complete blood count (CBC) with white blood cell (WBC) differential and platelet count.
5. Serum chemistry tests including: alanine aminotransferase (ALT), aspartic aminotransferase (AST), alkaline phosphatase (AP), lactic acid dehydrogenase (LDH), blood urea nitrogen (BUN), creatinine and total bilirubin;
6. Viral and serological tests including: testing for HBsAg, and for antibodies to HAV, HBcAb, HBsAb, HCV, HIV-1/HIV-2 (only if seronegative at baseline) and parvovirus B19 by routine immunoassay (only in subjects who are seronegative at baseline);
7. A sample of venous blood will be drawn from which approximately 5 mL of serum will be prepared and aliquoted into three vials of at least 1.5 mL of sample each. The samples will be frozen and retained at -20°C in the event that they are required for later serological or virology tests.

If at any quarterly visit, **the subject tests positive for the presence of Factor VIII inhibitors (inhibitor titer of greater than 0.6 modified BU/mL), based upon the value determined by the central reference laboratory**, the procedures specified in section 7.12 (Subjects Who Develop Inhibitors) will also be performed.

Contains Confidential and Proprietary Information of Grifols Inc.

7.5 Unscheduled Visits

For each unscheduled visit, the following tests will be performed:

1. Abbreviated physical examination including: interim medical history, vital signs (pulse, respiratory rate, oral temperature, blood pressure) and weight;
2. Factor VIII coagulant activity (Factor VIII:C);
3. Factor VIII inhibitor levels (BU/mL) in two sets of samples **(to be performed only if: a) there is clinical indication that the normal dosage of Alphanate® is not providing adequate hemostasis, or b) surgery;**
4. Hematologic status will be assessed by: complete blood count (CBC) with white blood cell (WBC) differential and platelet count;
5. Serum chemistry tests including: alanine aminotransferase (ALT), aspartic aminotransferase (AST), alkaline phosphatase (AP), lactic acid dehydrogenase (LDH), blood urea nitrogen (BUN), creatinine and total bilirubin;
6. Viral and serological tests **(to be performed only if subject exhibits clinical or subjective symptoms indicating possible viral infection)** including: testing for HBsAg, and for antibodies to HAV, HBcAb, HBsAb, HCV, HIV-1/HIV-2 (only if seronegative at baseline) and parvovirus B19 by routine immunoassay (only in subjects who are seronegative for parvovirus B19 at baseline);
7. A sample of venous blood will be drawn from which approximately 5 mL of serum will be prepared and aliquoted into three vials of at least 1.5 mL of sample each. The samples will be frozen and retained at -20°C in the event that they are required for later serological or virology tests.

If at an unscheduled visit, a test for Factor VIII **is positive for the presence of Factor VIII inhibitors (inhibitor titer of greater than 0.6 modified BU/mL), based upon the value determined by the central reference laboratory**, the procedures specified in section 7.12 (Subjects Who Develop Inhibitors) will be performed.

Contains Confidential and Proprietary Information of Grifols Inc.

7.6 In Hospital and In Clinic Treatments

A physician's qualitative assessment of hemostasis (evaluated as "None," "Moderate," "Good," or "Excellent") in response to therapy with Alphanate® received by the subject will be recorded for all treatments administered in the hospital, clinic, or at another location under the physician's direct supervision.

7.7 Home Treatment

Following enrollment, the subject will have the choice of obtaining Alphanate® treatment at the participating study site in response to bleeding episodes, or to receive treatment at home (See Section 7.9.1).

7.8 Miscellaneous

All enrollment tests should be performed prior to the first administration of Alphanate®. Samples drawn for quarterly testing will be drawn \pm 10 days of the scheduled visit date. The presence of inhibitors will be determined by the Nijmegen modification of the Bethesda assay (see below); the Factor VIII source for this assay will be normal pooled plasma. **Inhibitor titers will be considered valid if the subject's Factor VIII level is at or below baseline (less than 0.01 IU/mL)**, therefore, the subject should be scheduled for the quarterly visit at least three days after an infusion with Alphanate®.

If the subject's Factor VIII levels are higher than baseline at the time the plasma sample is drawn, then the subject will be rescheduled for testing within one week of the notification of the invalid result.

Assays for inhibitor to Factor VIII will be performed locally (i.e., at the coagulation testing laboratory for each clinical site) to support decisions regarding treatment. Duplicate plasma samples will be collected at each time point for confirmatory testing at a central reference laboratory. The central laboratory will utilize the Nijmegen modification of the Bethesda assay to improve reliability.¹⁷ The modification involves the following changes in reagents: (1) buffering of the normal pooled plasma used in the assay and control with 0.1 M imidazole to pH 7.4 and (2) replacing the imidazole buffer in the control mixture with immunodepleted Factor VIII-deficient plasma. In addition, to further improve the accuracy of the assays, a standardized immunodepleted plasma will be used for the performance of the assay at all clinical sites, as well as at the central reference laboratory.

The local laboratories will not be required to test for Factor VIII inhibitors using the Nijmegen modification of the Bethesda assay, but are required to provide the sponsor with a detailed description of the procedure used.

Contains Confidential and Proprietary Information of Grifols Inc.

Only the results of the assays from the central reference laboratory will be used in the determination and analysis of the primary endpoint for the clinical trial.

To determine the risk of transmission of parvovirus B19, subjects who are seronegative at enrollment will be tested approximately one week after receiving the first infusion with Alphanate[®] for the presence of parvovirus B19 by Polymerase Chain Reaction (PCR) testing.

